#### **4.2.3. Sensitivity analyses**

If more than 5% of the ES participants with immunogenicity results after study intervention are excluded from the PPS, the confirmatory analyses (refer to Section 2) will be repeated on the ES.

Within groups assessment for the PPS will be repeated by sex and study sites.

### **4.3. Secondary Endpoint(s) Analyses**

Refer to Section 4.5 for safety analyses.

Analyses on the immunogenicity endpoints will be conducted primarily on the PPS.

#### **4.3.1. Within groups assessment**

The following calculations will be performed.

For each group, at Visit 1 and Visit 3 time point,

- The percentage of participants with anti-RV IgA antibody concentrations  $\geq 90$  U/mL and their exact 95% CI will be computed.
- The distribution of anti-RV IgA Ab concentrations at Visit 3 will be displayed using reverse cumulative curves for the PPS.

#### **4.3.2. Between group assessment**

- The asymptotic standardized 95% CI for the difference in the percentage of participants with anti-RV IgA antibody concentrations  $\geq 90$  U/mL at Visit 3 between *Rotarix* PCV-free minus *Rotarix* will be computed.

#### **4.3.3. Sensitivity analyses**

If more than 5% of the ES participants with immunogenicity results after study intervention are excluded from the PPS, the confirmatory analyses (refer to Section 2) will be repeated on the ES.

Within groups assessment for the PPS will be repeated by sex and study sites.

#### 4.4. Tertiary/Exploratory Endpoint(s) Analyses

There are no tertiary/exploratory endpoints in this study

#### 4.5. Safety Analyses

The analyses will be descriptive and conducted on the ES.

The following calculations will be performed for each group:

- The percentage of doses and participants reporting at least 1 AE (solicited or unsolicited) during the 14-day (Day 1 to Day 14) solicited follow-up period will be computed, along with exact 95% CI. The same calculations will be done for AEs (solicited or unsolicited) rated as grade 3 in intensity and for AEs leading to a medically attended visit.
- The percentage of doses over the study and the percentage of participants (by dose and over the study) reporting each individual solicited systemic event will be computed, over the 14-day (Day 1 to Day 14) solicited follow-up period, following study intervention administration, along with exact 95% CI. The same calculations will be done for each individual solicited systemic event rated as grade 3 (grade 3 or grade 4 for fever) in intensity and events leading to a medically attended visit. Temperature above specific thresholds will also be summarized with threshold defined by half degree increment.

*Note: Intensity of fever will be assessed by considering the grading scales recommended by the Chinese authorities [NMPA 2019b].*

- The verbatim reports of unsolicited AEs will be reviewed by a physician and will be coded according to MedDRA. Every verbatim term will be matched with the appropriate Preferred Term. The percentage of participants with unsolicited AEs occurring within 31-day (Day 1 to Day 31) follow-up period after any dose with its exact 95% CI will be tabulated by Preferred Term. The same calculations will be done for each AE rated as grade 3 in intensity, for AEs leading to a medically attended visit and for AEs causally related to HRV as per the investigator assessment.
- The percentage of participants reporting the occurrence of SAEs (any, related, fatal, fatal related) from Dose 1 of the study intervention up to study end with its exact 95% CI will be tabulated by study group and by preferred term.
- The percentage of participants reporting the occurrence of SAEs (any, related, fatal, fatal related) within 31-day (Day 1 to Day 31) follow-up period after any dose with its exact 95% CI will be tabulated by study group and by preferred term.
- SAEs and drop outs due to AEs will be described in detail.

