9.4.4.1. Within groups assessment

The following calculations will be performed for each group:

- The percentage of doses and participants reporting at least 1 AE (solicited or unsolicited) during the 14-day (Day 1 to Day 14) solicited follow-up period will be computed, along with exact 95% CI. The same calculations will be done for AEs (solicited or unsolicited) rated as grade 3 in intensity and for AEs leading to a medically attended visit.
- The percentage of doses and participants reporting each individual solicited systemic event will be computed, over the 14-day (Day 1 to Day 14) solicited follow-up period, following study intervention administration, along with exact 95% CI. The same calculations will be done for each individual solicited systemic event rated as grade 3 in intensity and events leading to a medically attended visit. Temperature above specific thresholds will also be summarized with threshold defined by half degree increment.

Note: Intensity of fever will be assessed by considering the grading scales recommended by the Chinese authorities [NMPA, 2019b].

- The verbatim reports of unsolicited AEs will be reviewed by a physician and will be coded according to MedDRA. Every verbatim term will be matched with the appropriate Preferred Term. The percentage of participants with unsolicited AEs occurring within 31-day (Day 1 to Day 31) follow-up period after any dose with its exact 95% CI will be tabulated by preferred term. The same calculations will be done for each AE rated as grade 3 in intensity, for AEs leading to a medically attended visit and for AEs causally related to HRV as per the investigator assessment.
- The percentages of participants who started taking at least 1 concomitant medication, by type (any, antipyretic), from Day 1 to Day 14 after study intervention administrations will be tabulated with exact 95% CI. The percentages of participants who started taking at least 1 concomitant medication, by type (any, antipyretic), within 1 month after each dose will also be tabulated with exact 95% CI.
- SAEs and drop outs due to AEs will be described in detail.

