
 
• To assess the immunological non-inferiority of Rotarix PCV-free as compared to Rotarix in terms of percentage of participants with anti-RV IgA antibody concentrations ≥ 90 U/mL 1 month post Dose 2. 
 
– Non-inferiority will be demonstrated if the lower limit of the two-sided asymptotic standardized 95% CI for the difference in the percentage between the Rotarix PCV-free and Rotarix is greater than or equal to -10%.
 
 
 
	
Evaluation of immunogenicity in terms of anti-RV antibody concentrations.
 
 
• Percentage of participants with serum anti-RV IgA antibody concentrations ≥ 90 U/mL 1 month post Dose 2 in Rotarix PCV-free and Rotarix groups.
 

 
• To evaluate the reactogenicity of Rotarix PCV-free and Rotarix in terms of solicited systemic events.
 
• To assess the safety of Rotarix PCV-free and Rotarix in terms of unsolicited AEs and serious adverse events (SAEs).
 
	
 
• Solicited AEs 
 
– For each solicited systemic event, percentage of participants reporting the occurrence of the event within 14 days (Day 1- Day 14) after each study intervention administration.
 
 
 
• Unsolicited AEs 
 
– Percentage of participants reporting the occurrence of unsolicited AEs within 31 days (Day 1- Day 31) after each study intervention administration, according to the
 
 
 

Objectives	Endpoints**
	
Medical Dictionary for Regulatory Activities (MedDRA) classification.
 
 
SAEs 
 
Percentage of participants reporting the occurrence of SAEs from Dose 1 of the study intervention up to study end.
 
 
 

Ab = Antibody; AE = Adverse event; CI = Confidence Interval; IgA = Immunoglobulin A; GMC = Geometric mean Ab concentration; MedDRA = Medical Dictionary for Regulatory Activities; PCV = Porcine circovirus; PCV-free = No detection of PCV-1 and PCV-2 according to the limit of detection of the tests used; SAE = Serious adverse event; RV = Rotavirus; U = Unit; mL = milliliter

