#### 4.2.1. Within groups assessment

The following calculations will be performed.

For each group, at Visit 1 and Visit 3 time point,

- Seropositivity (at Visit 1 and Visit 3) and Seroconversion rates (at Visit 3) and their exact 95% confidence interval (CI) will be computed using the method of Clopper and Pearson [[Clopper](#), 1934],
- GMCs and their exact 95% CIs will be computed,

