#### 6.1.5. Study Intervention Compliance

The number of doses administered will be tabulated for each group for the ES. A dose is defined as a vaccination visit. Accordingly, a visit at which a replacement dose was given

following regurgitation will be counted as one dose. Note that participants without a replacement dose administered despite regurgitation will be summarized among the important protocol deviation summary.

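### The exact 95% CIs planned for percentages of doses treat an infant's two doses as independent, and for events that are not rare they under-cover if those doses are positively correlated (minor).

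*SAP*

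**What the plan says.** SAP 4.5 covers the 14-day period after each dose, by group. Its first bullet gives "The percentage of doses and participants reporting at least 1 AE (solicited or unsolicited" with an exact 95% CI, and repeats this for grade 3 events and for events leading to a medically attended visit. Its second bullet gives "The percentage of doses over the study and the percentage of participants (by dose and over the study) reporting each individual solicited systemic event", again with exact 95% CIs and with grade 3 and medically attended versions.

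Protocol 9.4.4.1 plans the same kind of row: "The percentage of doses and participants reporting each individual solicited systemic event will be computed", with exact CIs.

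Four other places set the scope:

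- **Unit.** SAP 6.1.5 says "A dose is defined as a vaccination visit", so a replacement after regurgitation does not add a dose. Two doses per infant are planned (Protocol 4.3).
- **Method.** SAP 4.5 does not name the exact method. SAP 4.2.1 says that the intervals for seropositivity and seroconversion "will be computed using the method of Clopper and Pearson".
- **Endpoint.** The reactogenicity endpoint in SAP 1.1 is the "percentage of participants reporting the occurrence of the event within 14 days" after each administration. Its unit is the participant, not the dose.
- **Status.** SAP 4.5 opens with "The analyses will be descriptive and conducted on the ES".

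Neither document mentions clustering, repeated measures or a design effect for the dose-level rows.

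**The concern.** An exact binomial interval has its stated coverage only when the observations are independent. In a row that pools doses, most infants appear twice. The two appearances share the infant and usually the parent who fills in the diary, and three of the six solicited events (loss of appetite, irritability/fussiness, cough/runny nose) are graded by the parent on a judgement scale (Protocol Table 18). Positive correlation within an infant is therefore plausible. If it is present, the effective sample size is below the number of doses and the interval is too short.

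What is at stake is the stated precision of these rows in the study report. No between-group safety comparison is planned, so the interval is the only measure of precision attached to them.

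**Working it through.** The documents give no coverage figure, event rate or within-infant correlation, so there is no planned figure to reproduce for this point. The correlation ρ and the event rate p below are assumptions, shown over a range.

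**Inputs**

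- Infants per group: 1000 (SAP 5; 1500 / (1 − 0.25) = 2000 in total, which agrees with the plan).
- Doses per infant: 2, so at most 1000 × 2 = 2000 doses per group.
- Interval: Clopper-Pearson, two-sided 95%, on 2000 doses (assumed from SAP 4.2.1).
- ρ = 0, 0.1, 0.3, 0.5, with p from 0.1% to 30%.

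**Step 1: variance.** For a common rate p at both doses,

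- P(event after both doses) = p² + ρp(1 − p)
- P(event after exactly one dose) = 2[p − P(both)]
- variance of an infant's total = 2p(1 − p)(1 + ρ), against 2p(1 − p) under independence.

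Example with p = 0.30 and ρ = 0.3: P(both) = 0.09 + 0.3 × 0.21 = 0.153, P(one) = 2 × (0.30 − 0.153) = 0.294, P(none) = 0.553. The variance per infant is 0.294 + 4 × 0.153 − 0.6² = 0.546, against 0.42 under independence, a ratio of 1.3 = 1 + ρ.

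**Step 2: width.** A correct interval is wider by √(1 + ρ): 1.05, 1.14 and 1.22 for ρ = 0.1, 0.3 and 0.5. Clopper-Pearson half-widths on the effective number of doses, 2000 / (1 + ρ), in percentage points:

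| Rate | ρ = 0 (as planned) | 0.1 | 0.3 | 0.5 |
|---|---|---|---|---|
| 30% | 2.03 | 2.13 | 2.32 | 2.50 |
| 10% | 1.34 | 1.41 | 1.53 | 1.65 |

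**Step 3: coverage of the planned interval.** The distribution of the total number of event-doses was enumerated exactly for 1000 infants, each contributing 0, 1 or 2, and the Clopper-Pearson interval on 2000 doses was checked against p (coverage in %):

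| Rate | ρ = 0 | 0.1 | 0.3 | 0.5 |
|---|---|---|---|---|
| 30% | 95.2 | 94.1 | 91.7 | 89.3 |
| 10% | 95.6 | 94.5 | 92.3 | 90.0 |
| 5% | 96.0 | 95.0 | 92.8 | 90.6 |
| 1% | 95.8 | 94.7 | 92.5 | 90.2 |
| 0.5% | 97.6 | 96.8 | 95.2 | 93.4 |
| 0.2% | 96.1 | 95.1 | 92.9 | 90.2 |
| 0.1% | 98.3 | 97.8 | 96.9 | 96.0 |

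The normal approximation 2Φ(1.96 / √(1 + ρ)) − 1 gives 93.8, 91.4 and 89.0% for ρ = 0.1, 0.3 and 0.5, in line with the 30% row.

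**Step 4: robustness.** With unequal rates at the two doses (35% and 25%), simulated coverage of the pooled interval is 94.1, 91.8 and 89.4% for ρ = 0.1, 0.3 and 0.5. With negative correlation (ρ = −0.1, 30% rate) the interval over-covers, at 96.3%. At rates of 0.5% and below, the discreteness of the exact interval can hide the effect, but not dependably: compare the 0.2% row with the 0.1% row.

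**Step 5: reading the groups side by side.** At equal true rates of 30%, the two groups' planned intervals fail to overlap in 0.5, 0.7, 1.4 and 2.2% of trials for ρ = 0, 0.1, 0.3 and 0.5. An informal overlap check is therefore not badly misled.

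**The case against.** The strongest objection is that the deciding input is not in the documents. With a small correlation nothing visible happens: at ρ = 0.02 coverage is 95.0% at a 30% rate and 95.4% at 10%, and at ρ = 0.05 it is 94.6% and 95.1%. At ρ = 0.1 the shortfall at a 30% rate is 0.9 points of coverage, or about 0.1 percentage point of half-width. The figures near 90% need ρ = 0.5, which nothing in the documents supports. This stands, and it is why the finding is conditional.

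Pooling over the study is stated only for the individual solicited events ("The percentage of doses over the study and the percentage of participants (by dose and over the study"). For the any-AE rows, and in Protocol 9.4.4.1, it is the natural reading but is inferred. The absence of a cluster adjustment and the use of Clopper-Pearson are likewise inferred from the word exact with nothing further specified. These points stand as limits on what the text proves.

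The plan also supplies unaffected estimates. For each solicited event the same bullet reports participants by dose and over the study, with one observation per infant, and the hypotheses in SAP 2 concern immunogenicity only. This is correct and keeps the point minor. It does not make the interval on the remaining rows right.

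Finally, the effective-sample-size interval offered below is not perfect for very rare events. At a 0.2% rate and ρ = 0.5 it covers about 93.5 to 93.7% in simulation. That is below nominal, though closer than the planned interval's 90.2%.

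**Conclusion.** The concern holds as a minor, conditional point. As written, the percentage-of-doses intervals rest on independence between an infant's two doses, which the plan neither states nor justifies. If the correlation is positive and larger than the slack in the exact interval (about 0.02 at a 30% rate, 0.05 at 10% and 0.1 at 1 to 5%), the intervals cover less than 95% for events that are not rare. For rates of 1 to 30%, coverage is about 92 to 93% at a correlation of 0.3 and about 89 to 91% at 0.5.

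This assumes Clopper-Pearson intervals, doses pooled within the row, and 1000 infants per group each receiving both doses. It does not extend to rare grade 3 or medically attended rows in general. It touches no declared endpoint, participant-level table or confirmatory conclusion, and no claim of a false difference between groups is made.

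**What to change.** Keep the exact CI for percentages of participants, by dose and over the study. For percentages of doses, add one sentence to SAP 4.5 that takes one of two routes:

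1. Report the percentage without a CI. This is the simplest route, and it loses little because the participant rows carry the endpoint.
2. Report a CI that clusters on infant, either with a robust (GEE) variance or as a Clopper-Pearson interval on the effective sample size. For the latter, let infant *i* have mᵢ doses and yᵢ event-doses, with M = Σmᵢ and p̂ = Σyᵢ / M. The design effect is [Σ(yᵢ − p̂mᵢ)² / M²] / [p̂(1 − p̂) / M], floored at 1, and the effective size is M divided by it. The SAP should also say what is done when a row has no events, for example setting the design effect to 1.

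In simulation (100,000 groups per setting), the effective-sample-size interval covered 95.2% to 97.5% for rates of 0.5, 1, 5, 10 and 30% and correlations of 0 to 0.5. Below 0.5% it can fall short, so dropping the CI is cleaner for very rare rows.

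The SAP should also name the exact method used in 4.5 and say whether the any-AE dose row is pooled over both doses.

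The cost is a small programming change and dose-level intervals about 5 to 22% wider for correlations of 0.1 to 0.5. Participant-level tables do not change.

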	
 • Evaluation of immunogenicity in terms of anti-RV antibody concentrations. 
 • Anti-RV IgA Ab seroconversion rate* 1 month post Dose 2 in the Rotarix PCV-free and Rotarix groups. • Serum anti-RV IgA Ab concentrations expressed as GMCs 1 month post Dose 2 in the Rotarix PCV-free and Rotarix groups. • *Seroconversion rate is defined as the percentage of participants who were initially seronegative (i.e., with anti-RV IgA Ab concentration < 20 U/mL prior the first dose of Rotarix) and developed anti-RV IgA Ab concentration ≥ 20 U/mL at Visit 3 (1 month post Dose 2). 
 • Evaluation of immunogenicity in terms of anti-RV antibody concentrations. 
 • Percentage of participants with serum anti-RV IgA antibody concentrations ≥ 90 U/mL 1 month post Dose 2 in Rotarix PCV-free and Rotarix groups. 
 • Solicited AEs 
 – For each solicited systemic event, percentage of participants reporting the occurrence of the event within 14 days (Day 1- Day 14) after each study intervention administration. • Unsolicited AEs 
 – Percentage of participants reporting the occurrence of unsolicited AEs within 31 days (Day 1- Day 31) after each study intervention administration, according to the Medical Dictionary for Regulatory Activities (MedDRA) classification. • SAEs 
 – Percentage of participants reporting the occurrence of SAEs from Dose 1 of the study intervention up to study end.

Ab = Antibody; AE = Adverse event; CI = Confidence Interval; IgA = Immunoglobulin A; GMC = Geometric mean Ab concentration; MedDRA = Medical Dictionary for Regulatory Activities; PCV = Porcine circovirus; SAE = Serious adverse event; RV = Rotavirus; U = Unit; mL = milliliter

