#### 6.1.4. Prior and Concomitant Medications

Summaries of co-administered vaccinations (i.e., vaccinations given on the day of each *Rotarix* dose) and intercurrent vaccinations (i.e., vaccinations other than *Rotarix* administered from birth up to Visit 3, excluding vaccination given on the day of *Rotarix* administration) will be provided for each group.

The percentages of participants who started taking at least 1 concomitant medication, by type (any, antipyretic), from Day 1 to Day 14 after study intervention administrations will be tabulated by group with the exact 95% CI.

The percentages of participants who started taking at least 1 concomitant medication, by type (any, antipyretic), within 1 month after each dose will also be tabulated by group with exact 95% CI.

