#### 6.2.6. Onset day

The onset day for an event (e.g. AE, medication, vaccination) is the number of days between the last study vaccination and the start date of the event. This is 1 for an event occurring on the same day as a vaccination (and reported as starting after vaccination).

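### The secondary unsolicited-AE endpoint is defined after each dose, but protocol 9.4.4.1 and SAP 4.5 plan it only after any dose (minor; descriptive safety analyses)

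*SAP*

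**What the plan says.** **Endpoint.** Protocol section 3, Table 3, lists as a secondary endpoint: "Percentage of participants reporting the occurrence of unsolicited AEs within 31 days (Day 1- Day 31) after each study intervention administration". SAP 1.1 repeats it. The solicited endpoint has the same construction in SAP 1.1, again tied to every dose given: "For each solicited systemic event, percentage of participants reporting the occurrence of the event within 14 days (Day 1- Day 14) after each study".

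**Planned analysis of unsolicited AEs.** Protocol 9.4.4.1 plans: "The percentage of participants with unsolicited AEs occurring within 31-day (Day 1 to Day 31) follow-up period after any dose". SAP 4.5, third bullet, carries this over: the percentage "within 31-day (Day 1 to Day 31) follow-up period after any dose with its exact 95% CI will be tabulated by Preferred Term". The grade 3, medically attended and related tables are to use the same calculations, so they too are after any dose.

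**Planned analysis of solicited events.** SAP 4.5, second bullet, states that "the percentage of participants (by dose and over the study) reporting each individual solicited systemic event will be computed".

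**Related items.** SAP 6.1.4 tabulates new concomitant medication "within 1 month after each dose will also be tabulated by group with exact 95% CI". SAP 6.2.6 defines onset day, which "is the number of days between the last study vaccination and the start date of the event". SAP 4.8 declares no change from the protocol's planned analysis.

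**The concern.** An endpoint and its analysis should describe the same quantity. Here the endpoint is worded per administration, while the analysis counts an infant once if an event falls in either dose's window.

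What would be lost is descriptive information. The pooled table cannot show whether unsolicited events are concentrated after one dose of this live vaccine, or whether the two arms look different after one dose only. The pooled figure also hides a difference in denominators. The Exposed Set needs only one dose, so it includes infants who never received Dose 2 and could not have had an event after it.

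**Working it through.** The plan gives no figure to reproduce for this point. The check sets the endpoint wording against every planned analysis that contains unsolicited AEs, and then asks whether the pooled percentage could stand in for the per-dose ones.

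**1. Endpoint against analysis**

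| Item | Endpoint wording (protocol Table 3, SAP 1.1) | Protocol 9.4.4.1 | SAP 4.5 or 6.1.4 |
|---|---|---|---|
| Solicited events, Days 1–14 | each administration | doses and participants; no split by dose stated | by dose and over the study |
| Unsolicited AEs, Days 1–31 | each administration | any dose | any dose |
| Concomitant medication, 1 month | not an endpoint | each dose | each dose |

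Of the two secondary endpoints worded per administration, only the solicited one is analysed by dose in the SAP.

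**2. Other analyses that contain unsolicited AEs**

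- SAP 4.5, first bullet: "The percentage of doses and participants reporting at least 1 AE (solicited or unsolicited) during the 14-day (Day 1 to Day 14) solicited follow-up period". This mixes solicited with unsolicited events, stops at Day 14, and is not split into Dose 1 and Dose 2. A percentage of doses pools both doses in one denominator.
- SAP 4.5, 31-day SAE table: after any dose, and SAEs only. The SAE endpoint itself runs from Dose 1 to study end, so it raises no each/any mismatch.
- SAP 4.6: no other analyses.

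None of these gives unsolicited AEs over Days 1 to 31 separately for each dose.

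**3. Does the pooled percentage determine the per-dose percentages?**

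Let p1 and p2 be the percentages after Dose 1 and Dose 2 on a common denominator. Then

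max(p1, p2) ≤ p(any) ≤ min(100%, p1 + p2).

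The pooled value only bounds the two components. As an illustration with assumed rates (the documents give none) and independence between doses:

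- p1 = 25%, p2 = 8%: p(any) = 1 − 0.75 × 0.92 = 31.0%.
- p1 = p2 = 17%: p(any) = 1 − 0.83 × 0.83 = 31.1%.

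Two very different profiles give almost the same pooled figure.

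**4. Can the split be made from data already collected?**

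Yes. The schedule of activities records unsolicited AEs after each dose, and SAP 6.2.6 counts onset from the last vaccination. One detail needs a rule. Dose 2 is allowed 28 to 48 days after Dose 1 (protocol Table 2, SAP 6.2.2). With Day 1 as the day of Dose 1, Dose 2 given d days later falls on Day d + 1:

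| d (days after Dose 1) | Day of Dose 2 in the Dose 1 window | Dose 1 days from which later events pass to Dose 2 |
|---|---|---|
| 28 | 29 | 29, 30, 31 |
| 29 | 30 | 30, 31 |
| 30 | 31 | 31 |
| 31 or more | 32 or later | none |

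Under the last-vaccination rule, the Dose 1 window therefore loses at most three of its 31 days, and only in infants given Dose 2 at 28 to 30 days.

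**The case against.** The best counter-argument is that the endpoint's wording only describes the collection window. The schedule of activities and protocol 10.3.6.1 both speak of recording AEs following each dose. On that reading, the percentage of infants with an event in either window reports the endpoint, and a split is an optional display. Protocol 9.4.4.1 lends some support, because it does not ask for solicited events by dose either; the SAP added that detail. This reading cannot be excluded. It is weakened by the SAP's own practice of reporting the parallel solicited endpoint by dose, and by the contrast between each and any elsewhere in the same documents.

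It is also fair to say that the practical loss is small. The analyses are descriptive and within group. The six solicited events, among them fever, diarrhea and vomiting, are already planned by dose over Days 1 to 14, and SAEs are to be described in detail. That stands, and it limits the point to a minor one.

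A reader might infer that the SAP departed from the protocol. It did not: protocol 9.4.4.1 already has the any-dose wording, so the statement in SAP 4.8 is not wrong on this item. The mismatch lies within each document.

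**Conclusion.** The mismatch is real and minor. Both documents define the unsolicited-AE endpoint per administration, both plan only a pooled tabulation, and neither plans a by-dose table. No hypothesis, alpha or power is affected. The size cannot be expressed as a trial figure, because the documents give no expected AE rates; the rates in the illustration are assumptions.

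Two stronger inferences are not supported. One is that the by-dose results will never be produced: output shells are not among the documents, and the data allow the split, so the most that can be said is that it is not planned here. The other is that a registered endpoint would go unreported: no registry record was examined, and the comparison is with the protocol's own Table 3.

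The conclusion assumes that the endpoint's per-administration wording means the same for unsolicited AEs as the SAP takes it to mean for solicited events.

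**What to change.** - In SAP 4.5, third bullet, report unsolicited AEs after each dose and after any dose, and apply this to the grade 3, medically attended and related versions.
- Use infants who received the dose in question as the by-dose denominator. Under SAP 4.1.2, infants with no reported event count as event-free, so keeping those without Dose 2 in the denominator would lower the Dose 2 percentage.
- Assign each event to the most recent dose, as in SAP 6.2.6, and state that for infants given Dose 2 at 28 to 30 days the Dose 1 window ends at Dose 2.
- Record the addition in SAP 4.8, or align protocol 9.4.4.1, so that the two documents do not diverge without a note.

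Rewording the endpoint in protocol Table 3 and SAP 1.1 to any dose would also remove the inconsistency, but it gives up the by-dose information.

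The cost is SAP wording, extra columns in tables already planned, and a slightly shortened Dose 1 window in a subset of infants. No new data are needed.
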